#### 4.1.1.6 FVIII Trough Levels

Trough levels = FVIII levels measured at Visit 6 (month 6) for all participants and for participants on 2x/week regimen at Visit 5 (month 3, 3-day trough).

Trough levels depend on the time since previous prophylactic infusion. All trough levels will be assigned to one of the following time intervals. Measurements outside of these intervals will be excluded from the analysis (outside of +/- 12 hours of target time point).

- 3 days: trough level measurement took place  $\geq 60$  -  $<84$  h after previous infusion
- 4 days: trough level measurement took place  $\geq 84$  -  $<108$  h after previous infusion
- 5 days: trough level measurement took place  $\geq 108$  -  $<132$  h after previous infusion
- 6 days: trough level measurement took place  $\geq 132$  -  $<156$  h after previous infusion
- 7 days: trough level measurement took place  $\geq 156$  -  $<180$  h after previous infusion
- 8 days: trough level measurement took place  $\geq 180$  -  $<204$  h after previous infusion
- 9 days: trough level measurement took place  $\geq 204$  -  $<228$  h after previous infusion
- 10 days: trough level measurement took place  $\geq 228$  -  $<252$  h after previous infusion

Validity rule for trough levels:

The following trough levels will be considered invalid: >37.5% after 3 days, >23.1% after 4 days, >21.5 after 5 and 6 days, >8.1% after 7 or more days.

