#### **8.5 Pharmacokinetics**

##### **8.5.1 Incremental Recovery and Trough Levels of Jivi**

Blood samples for Jivi incremental recovery, FVIII levels, and FVIII trough levels will be collected in all participants. Incremental recovery will be determined at Baseline (Day 1) by collecting a sample for FVIII level before the scheduled infusion and a second sample collected 15 to 30 minutes after end of the infusion. A third sample collected at a minimum of 4 hours after the end of the infusion to assess FVIII levels. The measurements should only be performed when the participant is not actively bleeding. If a participant is actively bleeding, the samples for incremental recovery will be postponed until the sample can be done after a prophylactic dose.

The exact sampling times before and after infusion and the dose administered will be documented in the CRF. Incremental recovery of Jivi is determined by measuring FVIII activity with a validated assay for FVIII.

Infusions given at study visits will be recorded in the site participant records, which will be the source documents and will be used to enter this information in the CRF.

All samples will be processed in the investigator's local laboratory. Plasma concentrations of FVIII will be measured using a validated FVIII activity assay.

Recoveries should be performed using the participants assigned treatment dose, rounded to full vial size.

At Month 3 (72 hours after the previous infusion), FVIII levels will be measured for all participants for the WAPPS-Hemo PK analysis. For participants on the twice weekly regimen, this will also serve as 1 of 2 trough level measurements (i.e. Day 3 of 2x/week regimen). At Month 6 [EOS]), samples for trough levels will be collected just prior to the scheduled infusion for all participants in alignment with the prophylaxis regimen (i.e. at Day 4 for 2x/week regimen, at Day 5 for Q5D regimen, and at Day 7 for less frequent regimens).

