### 1.1 Objectives and Endpoints

Objectives	Endpoints
Primary	
To assess the effect of using a baseline risk score, based on a participant's phenotypic and biologic variables, to select the most appropriate prophylaxis regimen for reaching a favorable outcome, when switching from a SHL product to Jivi	Occurrence of favorable outcome on the score selected dosing regimen
Secondary	
To assess the effectiveness of Jivi compared to a previous SHL treatment	ABR (total, joint, spontaneous) and change in total ABR from pre-study
To assess the frequency of Jivi administration	Change in the frequency of pre-study SHL treatment to the frequency of Jivi administration (infusions/month)
To assess the proportion of participants with 0 and $\leq 1$ spontaneous bleeds	Occurrence of participants with 0 and $\leq 1$ spontaneous bleeds
To assess participant quality of life (QoL) and physical activity, as measured by Patient Reported Outcomes (PROs)	Change in Haemophilia Quality of Life Questionnaire (Haem-A-QoL or Haemo-QoL KIDS, depending on age of participant); Patient's Global Impression of Change (PGI-C); EuroQoL 5 Dimensions (EQ-5D-5L) questionnaire; Treatment Satisfaction Questionnaire for Medication (TSQM); Work Productivity and Activity Impairment (WPAI) questionnaire scores
To assess target joint status, per International Society on Thrombosis and Haemostasis (ISTH) guidelines	Number of target joints and change in target joint status from baseline

Objectives	Endpoints
Other, Pre-specified	
To assess whether blood type and body mass index (BMI) would have led to a different score allocation	Participant score considering ABO type and BMI
To describe PK parameters derived from WAPPS-Hemo and assess any association with clinical risk score	PK parameters derived from WAPPS-Hemo
To determine participant Jivi trough levels while on a specific regimen	Trough measurement of Jivi levels
To determine the percentage of participants who can maintain > 1%, > 3 %, and > 5% FVIII trough levels while on a specific prophylaxis regimen	Occurrence of trough levels above 1%, 3% and 5%, stratified by prophylaxis regimen
Abbreviations: ABR = annualized bleeding rate; EQ-5D-5L = EuroQoL 5 dimensions; FVIII = human coagulation factor VIII; SHL = standard half-life	

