#### 4.4.3 Incremental Recovery and Trough Measurements of Jivi Levels

Actual sampling times before and after infusion and the dose administered will be presented in listings of FVIII levels. Incremental recovery FVIII levels will be presented with the corresponding participant weight value.

A summary of incremental recovery will be presented by risk group and also the frequency of samples failing validity criteria.

A summary of quantitative trough levels will be presented by risk group and also the frequency of trough levels above 1%, 3% and 5%.

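### The ±12 h trough rule cannot remove mistimed samples, and the shares above 1%, 3% and 5% count levels by risk group instead of participants by regimen

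*SAP*

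**What the plan says.** SAP 4.1.1.6 defines the samples: "Trough levels = FVIII levels measured at Visit 6 (month 6) for all participants and for participants on 2x/week regimen at Visit 5" (the 3-day level). It then says "All trough levels will be assigned to one of the following time intervals", lists windows for 3 to 10 days since the previous infusion, and adds "Measurements outside of these intervals will be excluded from the analysis (outside of +/- 12 hours of target time point". The validity limits also go by elapsed days: "The following trough levels will be considered invalid: >37.5% after 3 days, >23.1% after 4 days", then 21.5% for 5 and 6 days and 8.1% from 7 days on. Regimen appears in none of these three rules.

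SAP 4.4.3 gives the analysis: "A summary of quantitative trough levels will be presented by risk group and also the frequency of trough levels above 1%, 3% and 5" per cent.

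The objective in SAP 1.1 reads "To determine the percentage of participants who can maintain > 1%, > 3 %, and > 5% FVIII trough levels" while on a specific prophylaxis regimen. The endpoint beside it is the occurrence of trough levels above the three cut-offs, stratified by prophylaxis regimen.

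Protocol 8.5.1 places the Month 6 sample immediately before the next planned infusion: Day 4 for 2x/week, Day 5 for Q5D, and "at Day 7 for less frequent regimens".

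**The concern.** A tolerance of 12 h either side of a target works as a filter only if each participant has one target. Here there are eight, and any sample may take whichever it falls nearest. An off-schedule sample is relabelled to another day and kept. Because FVIII falls with time since infusion, a sample taken too early reads high against 1%, 3% and 5%, and one taken too late reads low.

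The second issue is the unit and the stratum. The objective is about participants on a regimen; the planned table counts levels in a risk group. The two differ for anyone with two levels and for anyone who has changed regimen. With 20 to 25 participants expected (SAP 5) across three regimens, a single misplaced or double-counted result visibly moves a percentage.

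**Working it through.** **Inputs.** Windows, trough definition and validity limits: SAP 4.1.1.6. Counting rule: SAP 4.4.3. Objective and endpoint: SAP 1.1. Sampling days: Protocol 8.5.1. Intervals of 3 and 4 days for 2x/week: Protocol Table 4-3. Sample size: SAP 5.

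**1. Reproduce the windows.** Each is 24 × d ± 12 h for d = 3 to 10: 60–<84, 84–<108, 108–<132, 132–<156, 156–<180, 180–<204, 204–<228, 228–<252 h. These match the SAP. Each upper bound equals the next lower bound, so the accepted range is continuous: 252 − 60 = 192 h. Only samples before 60 h or from 252 h on are excluded.

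**2. Compare with each regimen's own window.**

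| Sample | Protocol day ± 12 h | Also accepted earlier | Also accepted later |
|---|---|---|---|
| 2x/week, Visit 5 | 60–<84 h | 0 h | 252 − 84 = 168 h |
| 2x/week, Visit 6 | 84–<108 h | 84 − 60 = 24 h | 252 − 108 = 144 h |
| Q5D, Visit 6 | 108–<132 h | 108 − 60 = 48 h | 252 − 132 = 120 h |
| Q7D, Visit 6 | 156–<180 h | 156 − 60 = 96 h | 252 − 180 = 72 h |

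Each regimen's own window is 24/192 = 12.5% of what the rule accepts.

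**3. Validity limit.** A Q7D sample at 72 h is labelled 3 days and kept up to 37.5%. The limit for 7 days is 8.1%, and 37.5/8.1 = 4.6. The second check therefore does not catch what the first lets through.

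**4. How such samples can arise.** Visit 6 is also the early-withdrawal visit (Protocol 1.3 and 11.7.5). On withdrawal of consent, its activities take place when unused vials are returned (Protocol 1.3, footnote b), which need not fall at the end of a dosing interval. The mITT set needs only 4 months of follow-up, so it can include participants who withdraw after that.

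**5. Weight of 2x/week.** With N participants, k of them on 2x/week, there are N + k levels. For N = 20 and k = 5 there are 25 levels. The 2x/week participants supply 10/25 = 40% of levels but are 5/20 = 25% of participants.

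**6. Discordant pairs (constructed example).** Suppose all five are above 3% at 3 days and below it at 4 days. Levels above 3%: 5/10 = 50%. Participants above 3% at both: 0/5 = 0%. If 10 of the other 15 participants are above 3%, the pooled share is (5 + 10)/25 = 60% by level and 10/20 = 50% by participant.

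**7. Stratum.** Risk group fixes the assigned regimen (SAP Table 2), but regimen changes are allowed (Protocol 6.5). A low-risk participant moved to a more frequent regimen stays in the low-risk row of the 4.4.3 summary, beside 7-day troughs. The endpoint's strata are regimens.

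**8. Intervals longer than 7 days.** The less frequent interval is chosen by the investigator, with Q7D as an example (Protocol Table 4-2), and the SAP has windows to 10 days. For an interval above 7 days, a sample immediately before the next infusion and a sample on Day 7 are different samples. Protocol 8.5.1 asks for both in one sentence; 11.7.5 likewise pairs Day 7 with a visit as close as possible to the next infusion.

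**The case against.** The strongest reply is that the plan schedules its troughs correctly. Visit 6 is timed to the end of the dosing interval, and the 72 h Visit 5 levels of Q5D and less frequent participants are outside the trough definition. A reader might infer from the windows that mid-interval levels are routinely analysed as troughs. The documents do not support that: it needs a mistimed or early-withdrawal sample, and they give no rate for these. Actual sampling times will be listed.

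It can also be said that the day categories are meant for tabulation, that 4.4.3 never says they are merged, and that the table shells are in a separate document. That is fair and leaves the point partly open. But 4.4.3 does not mention a split by day either, and the exclusion sentence presents the windows as a filter, which they are not.

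A reader might further infer that the objective goes unanswered. It does not for Q5D and less frequent participants who stay on their regimen: each has one trough, so counting levels is counting participants. Nor is the 3-day level of 2x/week an early sample; it is a true trough at the end of a 3-day interval.

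Finally, it is tempting to attach a multiple to the effect of early sampling. No half-life for Jivi is given in the documents, and extreme assumptions defeat themselves. With a 12 h half-life, a 0.3% trough at 168 h would be 0.3 × 2^(96/12) = 77% at 72 h, which the 37.5% limit would void.

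**Conclusion.** The point holds in a limited form. The stated tolerance removes nothing between 60 and 252 h, so an off-schedule or early-withdrawal Visit 6 sample is kept and judged by the limit for its elapsed day. How many samples this touches cannot be known from the documents; scheduled ones on 2x/week, Q5D and Q7D are sound.

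The counting gap is certain in the SAP text but confined to 2x/week participants and regimen switchers. The 50% against 0% contrast shows what the rule permits; it is not a forecast, since it assumes that every pair straddles 3%. The weight of 40% against 25% assumes 5 of 20 participants on 2x/week.

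This is one of the other pre-specified endpoints in a study that is descriptive throughout and plans no formal comparison of regimens. It does not affect the primary result. It is worth correcting because the percentage reported may not be the one the objective names.

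**What to change.** **SAP 4.1.1.6.** Keep a level as a trough only if it lies within ±12 h of the end of the participant's prescribed interval at sampling: 72 h at Visit 5 and 96 h at Visit 6 for 2x/week, 120 h for Q5D, 168 h for Q7D. List the rest.

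For less frequent intervals longer than 7 days, first reconcile the two descriptions of the sampling time in Protocol 8.5.1 and 11.7.5. Until that is done, tabulate those Day 7 levels separately, so that samples taken as the protocol directs are not silently discarded.

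**SAP 4.4.3.** Report the percentage of participants above 1%, 3% and 5% by regimen at sampling. Count a 2x/week participant as maintaining a level only if all valid troughs exceed it, and summarise the 3-day and 4-day levels separately.

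**Cost.** SAP wording and, if needed, the table shells; the item on longer intervals also needs the protocol text reconciled. A few mistimed samples move from the table to a listing. No new data are required.

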In this proposed clinical study, the effect of using a new risk score approach, based on the best known predictive phenotypic and biologic variables, to select the most appropriate prophylaxis regimen for reaching a favorable outcome will be assessed for participants switching from SHL to Jivi. The scoring approach in this study has not yet been validated and is different from classical risk-based models in that the score allocation and the dosing regimen itself has an influence on the outcome of interest. Due to the nature of the study, the inclusion of sub-populations such as mild/moderate hemophilia patients, women, and patients with past FVIII inhibitors should not prevent them from participating.

The scoring approach will be composed of 5 individually weighted variables: pre-study bleeding phenotype, previous treatment frequency, number of active target joints, von Willebrand factor (vWF) antigen levels, and physical activity. These variables were selected on the basis of the existing data regarding their established or potential role in determining the most appropriate EHL regimen.

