**4.1.1.5 Incremental Recovery**

FVIII levels measured by a validated assay will be analyzed. Planned time points for assessment of incremental recovery are prior to start of infusion and 15 to 30 minutes after end of infusion.

Incremental recovery is calculated as shown below:

Incremental recovery =

(post-infusion FVIII level – pre-infusion FVIII level) \* weight (in kg)/ dose (in IU)

The most recent weight measurement will be used for calculation.

If a pre-infusion FVIII level value is below the lower limit of quantification (LLOQ), a data point with the value of one-half the LLOQ will be substituted.

A validity flag for incremental recovery values will be created. All incremental recoveries will be considered valid except when the following conditions apply:

- Pre-infusion FVIII >37.5% after 3 days, >23.1% after 4 days, >21.5 after 5 and 6 days, or >8.1% after 7 or more days
- Post-infusion FVIII value is below the LLOQ
- Post-infusion FVIII value is below Pre-infusion FVIII value

If an incremental recovery is flagged as not valid, then the corresponding pre-infusion, post-infusion and incremental recovery value will not be considered in tables displaying summary statistics of incremental recovery values and FVIII levels. FVIII levels that are not valid for calculation of incremental recovery will be listed.

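### The trough validity rule in SAP 4.1.1.6 has upper limits only, all above 5%; if flagged values are excluded, the shares above 1%, 3% and 5% can only fall or stay the same, and are biased downward if any flagged value is genuine

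*SAP*

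**What the plan says.** SAP 1.1 lists among the other pre-specified endpoints "Occurrence of trough levels above 1%, 3% and 5%, stratified by prophylaxis regimen". SAP 4.4.3 carries this out by risk group: a summary of the quantitative troughs and "also the frequency of trough levels above 1%, 3% and 5" per cent.

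SAP 4.1.1.6 applies two screens to a trough.

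- **Timing.** Each sample is assigned to a day by hours since the previous infusion. The consequence of failing is explicit: "Measurements outside of these intervals will be excluded from the analysis".
- **Value.** "The following trough levels will be considered invalid: >37.5% after 3 days", followed by limits of 23.1% at 4 days and 21.5 at 5 and 6 days, and then ">8.1% after 7 or more days". No lower limit, source or reason is given, and the text does not say what is done with an invalid trough.

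SAP 4.1.1.5 uses the same limits for pre-infusion levels, beginning "Pre-infusion FVIII >37.5% after 3 days". There the consequence is stated: the flagged values leave the summary tables of recovery and of FVIII levels, and are listed. SAP 4.4.3 plans a count of samples failing validity in its paragraph on incremental recovery, but none for troughs. No trough analysis on all values is planned.

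On who may enter, Protocol 2.1 supports "the inclusion of sub-populations such as mild/moderate hemophilia patients", and Protocol 5.1 sets no severity criterion.

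**The concern.** The exclusion criterion is the outcome itself. A value can be flagged only for being high, and each flagged value would have counted as above all three thresholds. If it is excluded, a success leaves both numerator and denominator.

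The 8.1% limit at 7 or more days matters most. It is the limit closest to 5%, and it applies to the low-risk group on the longest interval. A participant with mild or moderate hemophilia whose own FVIII exceeds 8.1% would have every 7-day trough flagged although the value is true. Slow clearance pushes the same way. Protocol 4.2 links higher vWF to lower FVIII clearance, and vWF of 150% or more lowers the risk score, which favors assignment to this group. The effect would therefore differ by regimen, which is how the endpoint is stratified. With no count of flagged troughs and no all-values result, the summaries would not show it.

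**Working it through.** The documents give no trough distribution and no expected share, so there is no plan figure to reproduce.

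**1. Direction (no assumption beyond exclusion).** Let n be the troughs in a group, k those above a threshold and m those flagged. The limits are 37.5%, 23.1%, 21.5 (printed without a percent sign) and 8.1%. All exceed 5%, so every flagged value is among the k at 1%, 3% and 5%. Exclusion moves the share from k/n to (k − m)/(n − m). The change is

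(k − m)/(n − m) − k/n = −m(n − k)/[n(n − m)],

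which is never positive. It is zero only if nothing is flagged or every trough is above the threshold.

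**2. Leverage at this sample size (illustrative k and m).** SAP 5 expects 20-25 participants, spread over three regimens.

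- n = 20, k = 14: 70.0% becomes 13/19 = 68.4% (m = 1), 12/18 = 66.7% (m = 2) or 11/17 = 64.7% (m = 3).
- A regimen group with n = 8, k = 5: 62.5% becomes 4/7 = 57.1% (m = 1) or 3/6 = 50.0% (m = 2).

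**3. Can a genuine 7-day value exceed 8.1%?** The dose of 60 IU/kg is from SAP Table 2. Recovery of 2.0-2.5% per IU/kg and single-phase decay after one dose are assumptions. The starting level is then 120-150%, and the half-life needed to reach 8.1% at 168 h is 168 × ln 2 / ln(120/8.1) = 43 h, or 168 × ln 2 / ln(150/8.1) = 40 h. Without own FVIII, that is twice or more the 16-20 h medians assumed in step 4. With own FVIII, no such half-life is needed.

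**4. Size at 7 days, share above 5%.** Simulation inputs, all assumed: median half-life 16 or 20 h with CV 35%; mean recovery 2.25% per IU/kg; 0 or 20% of participants with own FVIII of 1-15%; 0 or 5% of samples taken after an unrecorded infusion.

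| Half-life | Own FVIII | Unrecorded infusions | True | All values | After rule |
|---|---|---|---|---|---|
| 16 h | 0 | 0 | 1.4% | 1.4% | 1.0% |
| 20 h | 0 | 0 | 6.0% | 6.0% | 3.9% |
| 16 h | 20% | 0 | 16.0% | 16.0% | 5.8% |
| 20 h | 20% | 0 | 20.5% | 20.5% | 8.4% |
| 16 h | 0 | 5% | 1.4% | 6.3% | 1.0% |
| 20 h | 0 | 5% | 6.0% | 10.7% | 3.9% |
| 20 h | 20% | 5% | 20.3% | 24.3% | 8.3% |

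In the two rows with own FVIII and no unrecorded infusions, the share above 3% falls from 20.9% to 11.3% and from 29.1% to 18.3%. The share above 1% falls from 37.6% to 30.0% and from 56.4% to 49.8%.

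**5. Shorter intervals.** The effect is small. At 4 days with a 20 h half-life, the share above 5% goes from 39.3% to 38.2% without own FVIII, and from 49.7% to 48.3% with it. At 5 days with a 16 h half-life, 5% unrecorded infusions and no own FVIII, the truth is 8.4%, all values give 13.0% and the rule gives 8.7%. There the rule corrects.

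**6. Shape of the limits.** If they follow the day windows, the limit drops from 21.5 to 8.1 at 156 h. A trough of 15% would be valid at 155 h and invalid at 157 h. The SAP gives no reason for this step.

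**The case against.** The strongest defense is that the limits catch samples taken after an infusion nobody recorded. Most doses are self-administered at home and logged by the participant in the eDiary, so such samples are possible, and an implausibly high trough is their natural sign. This stands: in the rows with unrecorded infusions and no own FVIII, the rule lands closer to the truth than the all-values analysis.

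A reader might infer that the time windows already deal with mistimed samples, which would make the value limits redundant. They do not. The windows run without a gap from 60 to 252 h, so a sample at the wrong time within that span is reassigned to another day, not removed. They also depend on the recorded time of the previous infusion.

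It is also fair to say that exclusion is inferred. For troughs the SAP says only that the value is invalid; removal is written for timing and, in 4.1.1.5, for recovery. Exclusion is the natural reading, but the text needs to say so.

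The mild/moderate argument has limits too. Entry requires at least 150 exposure days and stable prophylaxis, and the documents do not say how many such participants to expect. Finally, the raw values are not hidden: SAP 4.1 lists all recorded data, and 4.4.3 lists FVIII levels with sampling times. What is missing is a count of flagged troughs and a summary that includes them.

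**Conclusion.** The point holds in conditional form. The limits are one-sided and all exceed 5%. If invalid troughs are excluded, the three shares can only fall or stay the same. That is downward bias if any flagged value is genuine, and a correction to the extent that flagged values come from unrecorded infusions. The FVIII value alone cannot show which applies.

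A reader might infer that the SAP certainly deletes these values and certainly understates the shares. The documents support neither: the consequence for troughs is unstated, and nothing shows what the flagged values will be. Nor do they support any single figure for the size. For example, a log-normal 7-day distribution with median 4% and log-SD 0.7 gives a fall from 37% to 26% above 5%, but that median is assumed. Under the step 3 recovery and decay assumptions, 4% at 7 days needs a half-life of about 32-34 h. Across the assumed scenarios without unrecorded infusions, the 7-day fall is about 2 points at a 20 h half-life without own FVIII (0.4 points at 16 h), and 10 to 12 points if 20% of participants have own FVIII of 1-15%.

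The material concern is confined mainly to the 8.1% limit at 7 or more days. The endpoint is descriptive and in the other pre-specified group; the primary endpoint is unaffected. This is a cheap improvement, not a flaw that threatens the trial's main result.

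**What to change.** Amend SAP 4.1.1.6 and 4.4.3 as follows.

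- State what happens to an invalid trough.
- Report the number of flagged troughs per regimen.
- Present the trough summaries and the shares above 1%, 3% and 5% twice: with all in-window values, and with flagged values excluded.
- Check each flagged value against the eDiary and CRF infusion record.

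The case for making either version the sole main analysis is debatable. Showing both avoids having to settle it and shows how much depends on the rule.

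The cost is SAP wording and one extra table. The downside is that the all-values version may include an occasional sample taken after an unrecorded infusion; the second version covers that case.
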